5.2.1.2 Per-Protocol Analysis Sets

5.2.1.2.1 Day 30 Per-Protocol Analysis Set

Groups 1 and 2

The Stage I Day 30 Per-Protocol Analysis Set (PPAS1) is a subset of Stage I Day 30 FAS (FAS1). Subjects with at least 1 of the following relevant protocol deviations will be excluded from the PPAS1:

- Subject did not meet all protocol-specified inclusion criteria or met at least 1 of the protocol-specified exclusion criteria
- Subject did not receive MenACYW conjugate vaccine according to randomization
- Preparation and/or administration of vaccine was not done as per-protocol
- Subject did not receive vaccine in the proper time window
- Subject did not provide a post-dose serology sample in the pre-specified time window at 30 (window, + 14) days post-vaccination
- Subject received a protocol-prohibited therapy/medication/vaccine that might impact antibody response to the study vaccine
- Subjects received study vaccine deemed unacceptable for use (e.g., because of a temperature excursion).
- Subject's post-vaccination serology sample did not produce a valid test result for any antigen (i.e., results for all antigens are missing)
- Any other deviation identified during conduct of the study and judged by the clinical team during data review as having a potential impact on the assessment of immunogenicity

5.2.1.2.2 Day 6 Per-Protocol Analysis Set *Groups 1 and 2*

The Day 6 PPAS (PPAS2) is a subset of Day 6 FAS (FAS2). Subjects with at least 1 of the following relevant protocol deviations will be excluded from the Day 6 PPAS:

- Subject did not meet all protocol-specified inclusion criteria or met at least 1 of the protocol-specified exclusion criteria
- Subject did not receive MenACYW conjugate vaccine according to randomization
- Preparation and/or administration of vaccine was not done as per-protocol
- Subject did not receive vaccine in the proper time window
- Subject did not provide a post-dose serology sample in the pre-specified time window at 6 (window, 5 to 7) days post-vaccination
- Subject received a protocol-prohibited therapy/medication/vaccine that might impact antibody response to the study vaccine
- Subjects received study vaccine deemed unacceptable for use (e.g., because of a temperature excursion).
- Subject's post-vaccination serology sample did not produce a valid test result for any antigen (i.e., results for all antigens are missing)
- Any other deviation identified during conduct of the study and judged by the clinical team during data review as having a potential impact on the assessment of immunogenicity.

5.2.1.3 Safety Analysis Set (SafAS1) *Groups 1 and 2*

The Stage I Analysis Set (SafAS1) is defined as those subjects who have received the study vaccine and have any safety data available. Safety will be analyzed according to the vaccine actually received by the subject.

Safety data recorded for a vaccine received out of the protocol design will be excluded from the analysis (and listed separately).

5.2.2 Stage II Analysis Sets (Groups 3 and 4)

5.2.2.1 Full Analysis Sets

The Stage II Day 30 FAS (FAS4) is defined as subjects in Groups 3 and 4 who received the study vaccine and have a valid serology result for at least 1 serogroup from a BL provided 30 (window, +14) days post-vaccination.

The Stage II FAS for persistence (FAS5) includes subjects in Groups 3 and 4 who have a valid serology result for at least 1 serogroup from a pre-vaccination BL (5-year antibody persistence).

5.2.2.2 Day 30 Per-Protocol Analysis Set

The Stage II Day 30 PPAS (PPAS3) is a subset of the Stage II Day 30 FAS (FAS4). Subjects with at least 1 of the following relevant protocol deviations will be excluded from the Stage II Day 30 PPAS:

- Subject did not meet all protocol-specified inclusion criteria or met at least 1 of the protocol-specified exclusion criteria
- Subject did not receive MenACYW conjugate vaccine according to randomization
- Preparation and/or administration of vaccine was not done as per-protocol
- Subject did not receive vaccine in the proper time window
- Subject did not provide a post-dose serology sample in the pre-specified time window at 30 (window, + 14) days post-vaccination
- Subject received a protocol-prohibited therapy/medication/vaccine that might impact antibody response to the study vaccine
- Subjects received study vaccine deemed unacceptable for use (e.g., because of a temperature excursion).
- Subject's post-vaccination serology sample did not produce a valid test result for any antigen (i.e., results for all antigens are missing)
- Any other deviation identified during conduct of the study and judged by the clinical team during data review as having a potential impact on the assessment of immunogenicity

5.2.2.3 Analysis Set (SafAS2)

The Stage II Analysis Set (SafAS2) is defined as those subjects who have received the study vaccine and have any safety data available. Safety will be analyzed according to the vaccine actually received by the subject.

Safety data recorded for a vaccine received out of the protocol design will be excluded from the analysis (and listed separately).

5.2.2.4 Enrolled Subjects

An enrolled subject is defined as a subject for whom a CRF has been created.

5.2.2.5 Randomized Subjects

A randomized subject is a subject for whom an injection vaccine group has been randomly allocated.

5.2.3 Populations Used in Analyses

5.2.3.1 Stage I

The primary immunogenicity analyses will be performed on the Stage I Day 30 PPAS (PPAS1) and will be confirmed on the Stage I Day 30 FAS (FAS1). In the FAS1, subjects will be analyzed by the vaccine group to which they were randomized.

The secondary immunogenicity analyses (Day 6 subset) will be performed on the Day 6 PPAS (PPAS2) and Day 6 FAS (FAS2).

The secondary antibody persistence analyses will be performed on the FAS3.

The safety analysis will be performed on the Stage I Analysis Set (SafAS1). Subjects will be analyzed according to the vaccine they actually received.

5.2.3.2 Stage II

Immunogenicity analyses will be performed on the Stage II Day 30 PPAS (PPAS3) and confirmed on the Stage II Day 30 FAS (FAS4).

The secondary antibody persistence analyses will be performed on FAS5.

The safety analysis will be performed on the SafAS2. Subjects will be analyzed according to the vaccine they actually received.

5.2.4 Subgroup Analysis

Subgroup analyses by age group (59 through 64 years of age and \geq 65 years), gender (female and male), and race (White, Asian, Black or African American, and Other) will be provided in Appendix 15 of the CSR.

5.3 Handling of Missing Data and Outliers

5.3.1 Safety

No replacement will be done. In all subject listings, partial and missing data will be clearly indicated as missing.

5.3.1.1 Immediate

For unsolicited non-serious systemic AEs, a missing response to the “Immediate” field is assumed to have occurred after the 30-minute surveillance period and will not be imputed.

For SAEs, missing or partially missing elapsed time from last vaccination recorded if within 24 hours will remain missing and not be imputed. Such SAEs will not be considered as immediate.

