4.4.2.2.4 Time of Onset

Time of onset is derived from the start date of the unsolicited non-serious AE provided in the clinical database and the date of last vaccination:

- start date of the unsolicited non-serious AE – date of previous vaccination

The time of onset should be considered as missing only if one or both of the dates are missing or partially missing.

Unsolicited non-serious AEs will be analyzed “Within 30 days,” which corresponds to AEs with a time of onset between D0 and D30 days after vaccination or missing. An AE with missing time of onset will be considered to have occurred just after the vaccination indicated by the visit number, so will be included in these tables.

Note: Unsolicited non-serious AE that occurred before vaccination (negative time of onset) or with a time of onset beyond 30 days, will not be included in analysis; but will be listed separately.

Time of onset will be displayed as follows:

- D0-D3
- D4-D7
- D8-D14
- \geq D15
- Missing

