5.3.1.2 Causality

Missing causality (relationship) for unsolicited non-serious AEs and SAEs will be considered at the time of analysis as related to vaccination.

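### A blank Immediate field is set to not immediate whatever the AE's start date: an imputation the SAP says it does not make, and one that can only lower the immediate-AE rate

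*SAP*

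**What the plan says.** SAP section 5.3.1.1 (Immediate) covers two kinds of event.

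- **Unsolicited non-serious systemic AEs.** A missing answer in the Immediate "field is assumed to have occurred after the 30-minute surveillance period and will not be imputed".
- **SAEs.** Where the elapsed time from the last vaccination, recorded for events within 24 hours, is missing or partial, it stays missing. Then: "Such SAEs will not be considered as immediate".

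The parent section, 5.3.1, opens with "No replacement will be done" and adds that subject listings will mark partial and missing data as missing.

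Two nearby rules handle other missing items. Under section 5.3.1.2, missing causality "will be considered at the time of analysis as related to vaccination". Section 4.4.2.2.4 says: "An AE with missing time of onset will be considered to have occurred just after the vaccination indicated by the visit number".

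Immediate unsolicited systemic AEs are the first safety endpoint listed in section 4.3.2.2. They have their own row in Table 5.2, which is limited to non-serious events. Section 4.3.2.3.1 describes the collection: subjects are observed for 30 minutes, and an unsolicited systemic AE in that time is marked as present with its details.

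**The concern.** The 30-minute observation exists to detect early reactions, and the immediate-AE percentage is where a reader looks for them. Under section 5.3.1.1 a gap in the record becomes a negative finding. The summary percentage does not show that the status was unknown, so a reported zero could cover an event whose timing nobody recorded.

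The text also misdescribes the step. It assigns a value and says in the same sentence that it does not impute, in a section that promises no replacement. A programmer could reasonably code the blank as No or leave it missing.

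The direction is the less cautious one. Missing causality, handled in the next subsection, is resolved towards counting the event. No reason is given for resolving a blank Immediate field the other way.

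**Working it through.** The SAP states no expected immediate-AE rate and no expected number of blanks, so there is no figure to reproduce. The check compares the rules and then illustrates the scale.

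**1. Direction.** The rule maps Yes to immediate, No to not immediate, and blank to not immediate. Let *a* be the number of subjects with a recorded immediate AE. Let *b* be the number whose only possible immediate AE has a blank field. The SAP reports *a*/*n*. The true value lies between *a*/*n* and (*a* + *b*)/*n*, so the rule always reports the lower bound.

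**2. What the start date adds.**

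- Start on Day 1 or later: the event cannot fall in the first 30 minutes, so No is correct.
- Start on Day 0: the event may or may not be immediate.
- Start date missing: unknown.

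The rule treats all three alike, although start dates are collected (section 4.3.2.3.3).

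**3. Comparison with the missing-onset rule.** Section 4.4.2.2.4 defines time of onset as "start date of the unsolicited non-serious AE – date of previous vaccination", a difference in days. It adds: "The time of onset should be considered as missing only if one or both of the dates are missing or partially missing". A blank Immediate field therefore does not make time of onset missing. The rule serves the 30-day tables, "which corresponds to AEs with a time of onset between D0 and D30 days after vaccination or missing".

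| Start date | Immediate field | Section 4.4.2.2.4 | Section 5.3.1.1 |
|---|---|---|---|
| Known | Blank | Onset in days from the dates | After 30 minutes |
| Missing | Answered | Placed just after vaccination | Not triggered |
| Missing | Blank | Placed just after vaccination | After 30 minutes |

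The two rules are in tension only in the last row.

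Section 5.3.1.5 says that time of onset is missing if either the start or the stop date is missing. That is wider than section 4.4.2.2.4, where only the start and vaccination dates count. Any repair of the Immediate rule should therefore use the start date itself and not the derived time of onset.

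**4. Scale.** Inputs: *n* = 180 planned in each of Groups 1 and 2, and *n* = 40 in each of Groups 3 and 4 (section 5.5); exact Clopper-Pearson 95% intervals (sections 5 and 5.1.3). Assumptions: *a* = 0, and the values of *b* shown.

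For *x* subjects out of *n*, the lower limit is the 0.025 quantile of Beta(*x*, *n* − *x* + 1), or 0 if *x* = 0. The upper limit is the 0.975 quantile of Beta(*x* + 1, *n* − *x*). For *x* = 0 the upper limit is 1 − 0.025^(1/*n*): 2.03% at *n* = 180 and 8.81% at *n* = 40.

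| *n* | *b* (assumed) | SAP rule | All *b* counted as immediate |
|---|---|---|---|
| 180 | 1 | 0% (0 to 2.03%) | 0.56% (0.01 to 3.06%) |
| 180 | 2 | 0% (0 to 2.03%) | 1.11% (0.13 to 3.96%) |
| 180 | 5 | 0% (0 to 2.03%) | 2.78% (0.91 to 6.36%) |
| 40 | 1 | 0% (0 to 8.81%) | 2.50% (0.06 to 13.16%) |
| 40 | 2 | 0% (0 to 8.81%) | 5.00% (0.61 to 16.92%) |

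Each affected subject is worth 1/180 = 0.56 percentage points in Group 1 or 2, and 1/40 = 2.5 points in Group 3 or 4.

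**The case against.** The best defence is how the field is filled in. Staff watch the subject for 30 minutes and actively mark an immediate event (section 4.3.2.3.1), so blanks should be few and a blank may well mean that nothing happened in that time. No event is lost either. The AE stays in the 30-day table and, if it began on Day 0, in the earliest onset category. SAEs stay in the 7-day and 30-day SAE rows of Table 5.2, and the listings mark missing data. The analysis is descriptive, and no hypothesis depends on it. Causality is an investigator's judgement on a recorded event, so its default need not govern a field completed under observation.

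Most of this stands, and it limits the size of the problem. It does not remove it. The SAP has a rule for a missing response but nowhere says that a blank is to be read as No. The listings do not correct the summary percentage.

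A reader might infer three stronger points that the SAP does not support:

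- **That section 5.3.1.1 contradicts the missing-onset rule in general.** That rule concerns missing dates, works in days and keeps events in the 30-day tables. The two meet only when both the date and the field are missing. Even then, an event attributed to a vaccination can begin after minute 30.
- **That every blank should count as immediate.** An AE starting on Day 1 or later cannot be.
- **That SAEs with missing elapsed time are wrongly left out of the immediate-AE rate.** The Table 5.2 row covers non-serious events only, so they do not belong in it.

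**Conclusion.** The point holds as a small, one-directional bias in a descriptive safety endpoint, together with wording that contradicts itself. That the rule can only lower the immediate-AE rate follows from the text and needs no assumption.

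The size is not known. With one affected subject and no recorded immediate AE in the group, both assumptions, 0/180 would be at most 1/180 and 0/40 at most 1/40. These figures use planned group sizes; the actual safety-set denominators may differ. If there are no blanks with a Day 0 or missing start date, there is no effect. The change is still worth making, because the information needed is already collected and a reported zero should not conceal an unknown.

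**What to change.** Rewrite section 5.3.1.1 as follows.

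- Set a blank Immediate field to No only when the AE start date is Day 1 or later.
- When the start date is Day 0 or missing, keep the field as Missing and show the number of such subjects and events as its own row in the immediate-AE table.
- Add a sensitivity count of immediate AEs with these events treated as immediate.
- Remove the wording that both assumes a value and denies imputing it. State the Day 1 rule as an exception to the no-replacement statement in section 5.3.1.
- For SAEs within 24 hours with missing or partial elapsed time, give the number with unknown immediate status in the SAE table. Do not add them to the non-serious immediate row.

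The cost is one revised rule, one extra row in the immediate-AE table, one sensitivity count and one count in the SAE table. No new data are needed. The downside is that the worst-case count may include an event that in fact began after 30 minutes, which a footnote can say.

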5.3.1.2 Causality

Missing causality (relationship) for unsolicited non-serious AEs and SAEs will be considered at the time of analysis as related to vaccination.

5.3.1.3 Measurements

Partially missing temperatures will be handled as described in [Section 4.4.2.1.1](#).

5.3.1.4 Intensity

For solicited reactions, missing intensities will be handled as described in [Section 4.4.2.1.1](#). For unsolicited non-serious AEs, missing intensities will remain missing and will not be imputed.

5.3.1.5 Start Date and Stop Date

Missing or partially missing start dates for unsolicited AEs will remain missing and not be imputed. If either the start or stop date is missing or partially missing, the time of onset will be considered to be missing. Nevertheless, unsolicited AEs with missing time of onset will be included in analyses according to the visit collected.

Missing or partially missing stop dates for AEs (solicited reactions and unsolicited AEs) will remain missing and not be imputed.

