4.3.2.3.3 Unsolicited Adverse Events

In addition to recording solicited reactions, subjects will be instructed to record any other medical events that may occur during the 30-day period after vaccination. Space will be provided in the diary card for this purpose.

Information on SAEs will be collected and assessed throughout the study, from inclusion until 30 days after vaccination. Any SAE occurring at any time during the study will be reported by the Investigator in the CRB according to the completion instructions provided by the Sponsor; this includes checking the “Serious” box on the AE CRF and completing the appropriate Safety Complementary Information CRFs. All information concerning the SAE is to be reported either as part of the initial reporting or during follow-up reporting if relevant information became available later (e.g., outcome, medical history, results of investigations, copy of hospitalization reports).

For each unsolicited AE (whether serious or non-serious), the following information is to be recorded:

- Start and stop dates^a
- Intensity of the event:

For measurable unsolicited AEs that are part of the list of solicited reactions, the size of the AE as well as the temperature for fever will be collected and analyzed based on the corresponding scale used for solicited reactions (see [Table 4.1](#) and [Table 4.2](#)).

All other unsolicited AEs will be classified according to the following intensity scale:

- Grade 1: A type of AE that is usually transient and may require only minimal treatment or therapeutic intervention. The event does not generally interfere with usual activities of daily living.
- Grade 2: A type of AE that is usually alleviated with additional therapeutic intervention. The event interferes with usual activities of daily living, causing discomfort but poses no significant or permanent risk of harm to the research participant.

^a The stop date of all related AEs will be actively solicited. For other events, the investigator will provide the stop date when it becomes available. AEs for which no stop date was obtained during the course of the study will be considered as ongoing at the end of the study.

- Grade 3: A type of AE that interrupts usual activities of daily living, or significantly affects clinical status, or may require intensive therapeutic intervention.

- Whether the AE was related to the investigational product (for unsolicited systemic AEs)

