4.3.2.4 Medically-Attended Adverse Events (MAAEs)

MAAE information will be collected throughout the study. MAAEs that occur from D0 to the D30 (+ 14 days) visit will be recorded as unsolicited AEs on the diary card as part of all unsolicited AEs collected for this post-vaccination period. An MAAE that occurs within the study period but meets the definition of an SAE should be reported only on the SAE Reporting Form, and not on the MAAE page of the CRF.

The Investigator will assess the causal relationship between the MAAE and the investigational or study product as either “Not related” or “Related,” as described in [Section 4.3.2.7](#).

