4.4.2.2.5 Duration

Duration is derived from the start and stop dates of the unsolicited non-serious AE provided in the clinical database:

- stop date of unsolicited non-serious AE - start date of unsolicited non-serious AE + 1.

The duration should be considered as missing only if the start and / or stop date of the unsolicited non-serious AE is missing or partially missing.

Duration will be displayed by period as following:

- 1-3 days
- 4-7 days
- 8-14 days
- \geq 15 days
- Missing

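### SAP 5.3.1.5 sets an unsolicited AE's time of onset to missing when only the stop date is absent, which contradicts the onset derivation in SAP 4.4.2.2.4

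*SAP*

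**What the plan says.** Three parts of the SAP bear on this.

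- **Onset derivation (4.4.2.2.4).** "Time of onset is derived from the start date of the unsolicited non-serious AE provided in the clinical database and the date of last vaccination". The formula is start date minus the date of the previous vaccination. The section then says: "The time of onset should be considered as missing only if one or both of the dates are missing or partially missing". In context, the dates meant are the start date and the vaccination date. AEs with a missing onset are treated as following the vaccination identified by the visit number and are kept in the 30-day tables. AEs that began before vaccination are handled differently, as are those "or with a time of onset beyond 30 days, will not be included in analysis; but will be listed separately".
- **Duration derivation (4.4.2.2.5).** Here the stop date is a real input: "The duration should be considered as missing only if the start and / or stop date of the unsolicited non-serious AE is missing" or incomplete.
- **Missing dates (5.3.1.5).** "If either the start or stop date is missing or partially missing, the time of onset will be considered to be missing". The next sentence reads: "Nevertheless, unsolicited AEs with missing time of onset will be included in analyses according to the visit collected". The section also says that missing stop dates are not imputed.

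Sections 4.4.2.3.2 and 4.4.2.4.2 apply the onset method of 4.4.2.2.4 to SAEs and MAAEs, so the conflict is not confined to non-serious unsolicited AEs.

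**The concern.** A missing stop date says nothing about when an event began. Section 5.3.1.5 nevertheless lets it erase a recorded start. The events concerned are foreseen in the SAP. A footnote in Section 4.3.2.3.3 says: "AEs for which no stop date was obtained during the course of the study will be considered as ongoing" at study end. The same footnote limits active pursuit of stop dates to related AEs, so the affected events should be mainly unrelated ones.

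Two things are at stake. First, time to onset is a named safety endpoint (4.3.2.2) and a descriptor in Table 5.2, and under 5.3.1.5 part of it would be reported as missing although the data exist. Second, events outside the 30-day window could enter the 30-day rates, because an AE stripped of its onset is included by visit. Two programmers who each follow a different section would produce different safety tables from the same database.

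**Working it through.** The SAP gives no figure to reproduce. The check applies both rules to each possible pattern of dates, with the vaccination date complete throughout.

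| AE dates | Rule in 4.4.2.2.4 | Rule in 5.3.1.5 |
|---|---|---|
| Start Day 5, stop missing | Onset 5, category D4-D7 | Onset missing; still in the 30-day tables |
| Start Day 35, stop missing | Onset 35; excluded and listed separately | Onset missing; included in the 30-day tables |
| Start before vaccination, stop missing | Negative onset; excluded and listed separately | Onset missing; included as if just after vaccination |
| Start missing | Onset missing | Onset missing |
| Start and stop complete | Onset known | Same onset |

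The rules differ in the first three rows, all of which have a known start and an absent or incomplete stop date. They agree in the last two. Because 4.4.2.2.4 says missing *only if*, Section 5.3.1.5 cannot be read as adding a further condition.

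**Can a start after Day 30 be in the database?** Yes.
- The post-vaccination visit is at Day 30 with a window of +14 days, so the latest visit is 30 + 14 = Day 44.
- Tables 3.2 and 3.3 have unsolicited AEs in Groups 1 and 2 reported throughout the study period. Table 3.4 has them recorded from Visit 2 through Visit 3 in Groups 3 and 4.
- For MAAEs, Section 4.3.2.4 is explicit: "MAAEs that occur from D0 to the D30 (+ 14 days) visit will be recorded as unsolicited AEs on the diary card".
- Section 4.4.2.2.4 itself provides for onsets beyond 30 days.

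The span in which such a start can fall runs from Day 31 to the visit. That is 0 days if the visit is on Day 30 and 44 − 30 = 14 days if it is on Day 44.

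**Size.**
- *Starts on Days 0 to 30.* The event is in the 30-day tables under both rules, so the count does not change. The event moves from one of the four dated onset categories (D0-D3, D4-D7, D8-D14, D15 or later) to the missing category.
- *Starts on Days 31 to 44.* The event moves from the separate listing into the 30-day tables. Suppose it is that subject's only unsolicited AE and group sizes are as planned. It then adds 1/180 = 0.56 percentage points to the rate in Group 1 or 2, and 1/40 = 2.5 percentage points in Group 3 or 4. These are the weights of one subject, not an expected effect.

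The number of such events cannot be computed from the SAP.

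**The case against.** The contradiction in the text is hard to dispute. The case on the other side is that it matters little.

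- **The effect on results is small.** For starts on Days 0 to 30, incidence, intensity and relatedness tables are identical under both rules. This stands.
- **The late-start case is narrow.** It needs a visit after Day 30, an AE beginning between Day 31 and that visit, its entry in the database, and no complete stop date. Subjects are asked to record events over a 30-day period (4.3.2.3.3), and Section 4.3.2.4 speaks only of MAAEs. The case is therefore probably rare, but the procedure tables carry unsolicited AE recording up to the visit, so it is not excluded.
- **Ongoing may not mean missing.** A programmer could treat an ongoing AE as having no stop date yet, rather than a missing one, which would shrink the affected set. The SAP does not draw that distinction, and the duration categories in 4.4.2.2.5 have no place for ongoing events, so they would most likely be handled as missing.
- **A programmer would probably follow 4.4.2.2.4.** It is the dedicated derivation section, it gives the formula, and the SAE and MAAE sections refer to it. This lowers the practical risk. It does not settle the matter, because no order of precedence is stated and 5.3.1.5 is the section on missing dates.

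**Conclusion.** The concern holds. Sections 4.4.2.2.4 and 5.3.1.5 give incompatible rules for an unsolicited AE with a known start and no complete stop date. Section 5.3.1.5 is the faulty one, since its start-or-stop condition fits duration and not onset. It may have been carried over from the duration rule, but that is an inference.

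The consequence is confined to descriptive safety output: onset categories for AEs with no complete stop date, and inclusion in the 30-day tables of any such AE that began after Day 30 or before vaccination. No hypothesis test or immunogenicity result is touched. The contradiction itself is certain. A material effect on reported rates is not, and the effect is probably small. The sizes given assume planned group sizes, an AE with no stop date treated as having a missing one, and a literal application of 5.3.1.5. The point should be corrected because a derivation rule is wrong as written and the correction is nearly free.

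**What to change.** In Section 5.3.1.5, remove the stop date from the onset rule and name the two dates that 4.4.2.2.4 uses. Suggested wording: *Time of onset is set to missing when the AE start date or the date of the preceding vaccination is missing or incomplete; an absent stop date does not affect it.* Keep the stop date for duration only, as 4.4.2.2.5 already does. The sentence on including AEs with missing onset by visit can stay, since it would then apply only where onset really is unknown.

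The cost is one sentence of SAP text. It needs no new data and no extra programming.
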